7.5.4.5 Sample Size Calculation

A sample size of 70 subjects with usable Holter telemetry data during the MARVEL 2 study procedures provides at least 90% power to test the primary safety hypothesis given the following assumptions:

1. One-sided type I error rate = 0.025
2. Single test of a proportion after all enrolled subjects have had an opportunity to complete the MARVEL 2 study procedures and have had their Holter data evaluated.
3. The proportion of subjects meeting the primary endpoint in the MARVEL 2 pacing mode will exceed 98%.

Justification of Sample Size Assumptions

It is expected that all (100%) subjects will meet the primary safety endpoint. Specifically, in the MARVEL study, no pauses exceeding two cardiac cycles (as defined by the lower pacing rate interval) and no oversensing induced tachycardia exceeding three minutes were observed.

7.5.4.6 Determination of Subjects/Data for Analysis

All available Holter recordings (including multiple recordings for subjects evaluated at multiple visits following initial Micra implant) with usable telemetry during MARVEL 2 adaptive mode will be included in the analysis.

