17.5.5 Determination of Subjects and Data for Analysis

All subjects with normal sinus node function and persistent 3rd degree AV block during Holter monitoring with at least 500 evaluable beats during VVI pacing and at least 500 evaluable beats during MARVEL 2 adaptive pacing in which the device is providing VDD pacing¹ will be included in the primary analysis for this objective. For *de novo* subjects, only data collected during the 20-minute resting period at pre-hospital discharge will contribute to the analysis of the primary objective. (Note that ancillary objective number five will compare the atrioventricular synchronous pacing rates observed at pre-hospital discharge and at 1-month post-implant.) However, if a *de novo* subject does not have usable Holter data at pre-hospital discharge, their Holter data approximately 1-month post-implant will be used in the analysis, if available.

¹ Cardiac cycles during MARVEL 2 adaptive mode pacing that occur during an AV conduction test will not be considered evaluable as the pacing mode is set temporarily to VVI40 while the device checks for intrinsic AV conduction.

Loss of communication between the Holter and the implanted Micra device, called telemetry dropout, can lead to loss of the marker indicating a ventricular event was sensed or a ventricular pace was delivered. Therefore, beats with no ventricular sense or pace markers and indication of telemetry dropout in the first 300 ms after a P-wave will be discarded (i.e. they are not evaluable beats).

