7.1.4 Usable Holter Datasets

A Holter dataset (i.e. device data telemetered to the Holter flash memory and surface ECG recordings) will be considered usable if there is readable telemetry signal as determined by the presence of visible device and algorithm marker channel. Additionally, to be included in the analysis of study objectives that require assessment of AV synchrony (i.e. primary efficacy objective, [REDACTED]

[REDACTED] visible P-waves must be present on the ECG recordings.

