7.5.4.3 Performance Requirements

The percentage of subjects meeting the primary safety endpoint is significantly greater than 87% (i.e. the lower two-sided 95% confidence interval for the estimate exceeds 87%). For example, in a sample size of 70 subjects with usable Holter datasets, this objective would be met if at least 67 of the 70 subjects (96%) meet the primary safety endpoint. Further, with a sample size of 70 subjects with usable Holter datasets the lower two-sided 95% confidence interval will be 94.9% if all 70 subjects meet the primary safety objective.

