7.5.4.7 Missing Data and Sensitivity Analyses

The primary source of missing data for this objective is anticipated to be Holter usability status and telemetry dropout during MARVEL adaptive mode pacing. Note that both sources of missing data can plausibly be assumed independent of primary safety endpoint status as Holter usability status is primarily related to electrode contact. However, to quantify the amount of missing data, the number of unusable Holter files and the proportion of beats during MARVEL 2 operation with telemetry dropout will be computed.

If Holter data from subjects who had the MARVEL 2 software downloaded is missing (e.g. deemed entirely unusable, Holter never placed on subject), it will be included in a tipping point analysis to determine the sensitivity of the statistical inference to the missing data. If the tipping point is less than the number of subjects with missing data, stochastic methods may be employed to aid in interpreting the likelihood the tipping would be achieved. Specifically, simulations from a Beta distribution with shape parameters based on the observed data will be used to compute the predictive probability of observing or exceeding the tipping point.

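### The primary safety analysis sets no minimum readable adaptive-mode telemetry, and the SAP pause screen passes over dropout intervals, so a barely observed subject counts as a full success and the pass rate can be inflated

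*SAP*

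**What the plan says.** **Endpoint.** Protocol 8.2.1.2 and SAP 7.5.4.1 ask for freedom from two kinds of software-related event (long pauses, and oversensing tachycardia lasting more than 3 minutes) over the full Holter period in which the features are enabled.

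**Entry.** SAP 7.5.4.6 states that recordings "with usable telemetry during MARVEL 2 adaptive mode will be included in the analysis"; protocol 17.6.5 is equivalent. SAP 7.1.4 says a dataset "will be considered usable if there is readable telemetry signal as determined by the presence of visible device and algorithm marker channel". Neither attaches a duration, beat count or study phase. The efficacy analysis, by contrast, requires 500 evaluable beats in each pacing mode (SAP 7.5.3.6).

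**Detection.** Protocol 17.6.4 searches the ventricular markers for long intervals and has each one reviewed on surface ECG to separate true pauses from dropout. SAP 7.5.4.4 flags a long interval only where no dropout is recorded, and only flagged intervals go to review. For high rates the same section takes the opposite course: a fast run is assumed to continue through a gap.

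**Missing data.** SAP 7.5.4.7 says that Holter data that "is missing (e.g. deemed entirely unusable, Holter never placed on subject), it will be included in a tipping point analysis". It treats missingness as independent of the endpoint because "Holter usability status is primarily related to electrode contact". Dropout is to be quantified as a proportion of beats. Protocol 17.6.6 promises tipping-point work if missing data become an issue, with no threshold.

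**The concern.** Each subject enters the exact binomial test as one unweighted success or failure. A subject with a few readable minutes and no detected event has the same weight as one followed through rest, posture changes and walking.

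The pause rule adds to this. A true pause inside a dropout gap never reaches the ECG reviewer under the SAP, although the surface ECG may show it. A subject whose readable events all lie within 3 minutes cannot fail the tachycardia component.

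The independence argument does not repair this. Dropout that is entirely unrelated to events still shortens observation and so misses events. Its stated reason also concerns something else: electrode contact bears on Holter usability, while protocol 17.5.5 describes dropout as "Loss of communication between the Holter and the implanted Micra device, called telemetry dropout".

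At stake is the error rate of a co-primary objective in a pivotal study.

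**Working it through.** **1. The plan's own figures.** Inputs from SAP 7.5.4.3 and 7.5.4.5: n = 70, performance goal 87%, "One-sided type I error rate = 0.025", success at 67 or more, planning rate 98%, power at least 90%.

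- Clopper–Pearson lower 95% limit: 87.98% at 67/70 (passes), 86.01% at 66/70 (fails), 94.87% at 70/70 (stated as 94.9%).
- Exact type I error: P(failures ≤ 3 | 70, 0.13) = 0.0145.
- Power: P(failures ≤ 3 | 70, 0.02) = 0.948.

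The stated design reproduces. These figures treat every subject as observed for the whole period.

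**2. Adding partial observation.** Let m subjects have readable coverage f and the other 70 − m be complete. The values of m and f are assumptions; the documents give neither. With a true failure probability of 0.13, the chance q that a short subject is seen to fail at f = 0.10 depends on how events arise:

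- A. Detection proportional to coverage: q = 0.13 × 0.10 = 0.0130.
- B. Constant event rate: q = 1 − 0.87^0.10 = 0.0138.
- C. Three independently detectable events per failing subject: q = 0.13 × (1 − 0.9³) = 0.13 × 0.271 = 0.0352.

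Then P(pass) = Σ(k = 0 to 3) P(Bin(m, q) = k) × P(Bin(70 − m, 0.13) ≤ 3 − k).

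| Short subjects at 10% coverage | A | B | C |
|---|---|---|---|
| 0 of 70 | 1.4% | 1.4% | 1.4% |
| 7 of 70 | 2.7% | 2.7% | 2.4% |
| 14 of 70 | 4.9% | 4.9% | 4.0% |

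The nominal 2.5% is reached or nearly reached with 7 short subjects and exceeded under all three models with 14.

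**3. At the planning rate.** With a true rate of 98% and model B, 7 short subjects at 10% coverage move the expected pass rate from 98.0% to (7 × 0.98^0.10 + 63 × 0.98)/70 = 98.2%, and the chance of passing from 94.8% to 96.1%. If no events occur, every subject passes whatever the coverage and nothing is inflated.

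**4. The two pause rules side by side.** Under protocol 17.6.4, a long interval goes to ECG review, and the review decides between pause and dropout. Under SAP 7.5.4.4, a long interval with dropout is set aside before review. The SAP's later review step is still asked to recognise dropout, although the screen has already removed the intervals where dropout was flagged. The two texts do not describe the same procedure.

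**The case against.** The case on the other side has real force, and several stronger readings do not survive it.

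- **That the pass rate is inflated.** A reader might infer this, but the documents do not show it. Both expect 100% success and report no qualifying events in the earlier MARVEL study (SAP 7.5.4.5). The most that can be said is that the rate can be inflated.
- **That the effect is large.** If all 70 subjects had reduced coverage and detection were proportional to it, P(pass) at 87% would be 5.8%, 11.0% and 32.5% at 80%, 70% and 50% coverage. With three independently detectable events per failing subject, the same cases give 1.5%, 1.8% and 3.5%. Nothing in the documents supports the larger set over the smaller.
- **That the dropout rules always favour the device.** Carrying a fast rate through gaps can join short runs into a flagged episode, which works against it. Manual review follows, and the point stands for tachycardia. It does not help with pauses.
- **That dropout rises with posture or walking.** Neither document says so.
- **That partial data are shut out of the tipping-point analysis.** The SAP gives its cases as examples, and both documents name dropout as a source of missing data. Still, the SAP's examples are subjects with no usable recording, and the protocol's trigger has no threshold, so nothing commits the analysis to partly observed subjects.
- **That the primary set should change.** Removing only event-free, low-coverage subjects would make inclusion depend on outcome. It could also cost power: with 63 subjects left, 61 must pass and power at 98% is 86.8%, below the stated 90%.

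The 500-beat rule is an imperfect comparison, because it supports estimation of a within-subject percentage and the first efficacy sensitivity analysis drops it. Parts of SAP 7.5.1, 7.5.2 and 7.5.4.4 are redacted, so a coverage rule there cannot be excluded. The unredacted usability and analysis-set definitions contain none.

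**Conclusion.** The point holds as a gap in specification. No readable minimum is set, the SAP pause screen is narrower than the protocol's, and the planned sensitivity analysis does not clearly reach partly observed subjects. For pauses, and for the missing minimum generally, lost observation can only turn a failure into a success.

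The size cannot be derived from the documents. The illustration (1.4% rising to about 2.7% with 7 subjects at 10% coverage, and to 4.0–4.9% with 14) rests on an assumed coverage pattern, an assumed detection model and a true pass rate exactly at 87%. At the planning rate the shift is about 0.2 percentage points for 7 such subjects, and it is zero if no events occur. This justifies an added sensitivity analysis and a reconciled pause screen, not a change to the primary test.

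**What to change.** Keep the primary analysis set and the exact binomial test.

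1. **SAP 7.5.4.7.** Pre-specify a sensitivity analysis in which event-free subjects whose readable adaptive-mode telemetry falls below a pre-set share (80%, for example) are treated as missing and added to the existing tipping-point analysis. A confirmed event counts as a failure whatever the coverage. With 70 subjects and 67 needed, the tipping point is 4 minus the confirmed failures. If wholly missing subjects are added, n exceeds 70 and the success rule must be recomputed. Because failures stay in the observed set while some event-free subjects leave it, the Beta-based predictive step will lean conservative and should be read as a stress test.
2. **SAP 7.5.4.4.** Align the pause screen with protocol 17.6.4, so that long intervals with dropout also go to surface-ECG review.
3. **Reporting.** Tabulate readable adaptive-mode time per subject and dropout by study phase.
4. **Rationale.** Do not rest the independence of telemetry dropout on electrode contact.

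The cost is SAP wording, one derived variable, some extra ECG review by the existing reviewers, and a sensitivity result that may be less favourable. The 80% share is a choice and should be fixed before the data are seen.

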7.5.4.7 Missing Data and Sensitivity Analyses

The primary source of missing data for this objective is anticipated to be Holter usability status and telemetry dropout during MARVEL adaptive mode pacing. Note that both sources of missing data can plausibly be assumed independent of primary safety endpoint status as Holter usability status is primarily related to electrode contact. However, to quantify the amount of missing data, the number of unusable Holter files and the proportion of beats during MARVEL 2 operation with telemetry dropout will be computed.

If Holter data from subjects who had the MARVEL 2 software downloaded is missing (e.g. deemed entirely unusable, Holter never placed on subject), it will be included in a tipping point analysis to determine the sensitivity of the statistical inference to the missing data. If the tipping point is less than the number of subjects with missing data, stochastic methods may be employed to aid in interpreting the likelihood the tipping would be achieved. Specifically, simulations from a Beta distribution with shape parameters based on the observed data will be used to compute the predictive probability of observing or exceeding the tipping point.

7.5.5 Secondary Objective

Demonstrate an increase in stroke volume, as measured by left ventricular outflow tract velocity time integral, with the MARVEL 2 software relative to VVI pacing in subjects with normal sinus node function and persistent 3rd degree AV block.

7.5.5.1 Endpoint Definition

The secondary endpoint is left ventricular outflow tract velocity time integral (LVOT VTI) as obtained from echocardiogram while the MARVEL 2 features are in adaptive mode (VDD pacing) and while the MARVEL 2 features are in monitor mode (VDI pacing which is effectively VVI pacing). This will be measured by the echo core laboratory.

7.5.5.2 Hypothesis

H₀: μ_{AV} = μ_{VVI}, versus

H_a: μ_{AV} ≠ μ_{VVI}

where μ_{AV} is the population mean LVOT VTI in the MARVEL 2 adaptive pacing mode and μ_{VVI} is the population mean LVOT VTI in MARVEL monitor mode (VVI pacing).

7.5.5.3 Performance Requirements

The sample mean LVOT VTI during MARVEL 2 adaptive pacing (VDD pacing) is significantly different and greater at the 0.05 level than the sample mean LVOT VTI during VVI pacing.

Meeting the performance requirement for the secondary objective will demonstrate that the MARVEL 2 features can increase cardiac stroke volume compared to VVI pacing in the population with normal sinus node function and persistent 3rd degree AV block.

7.5.5.4 Analysis Methods

Echocardiograms will be collected for each subject during MARVEL 2 adaptive pacing and during VVI pacing. To ensure that the echo core lab is blinded to subject and programmed pacing mode, randomly generated numbers will be used to label the echo recording medium. Specifically, a random 5-digit number ("echo id") will be assigned to label the echo recording medium and link the echo core lab results to an individual study subject. Additionally, to address any possible order effects, study sites will be randomized to perform the echo while the MARVEL 2 algorithm is programmed to Adaptive mode first followed by Monitor Mode second or while the MARVEL 2 algorithm is programmed to Monitor mode first followed by Adaptive mode. This strategy will blind the echo core lab personnel to study site, subject, and pacing mode and allow the "echo id" to link to the appropriate center, subject, and pacing mode.

The echo core lab will determine LVOT VTI for up to 6 cardiac cycles per programmed mode and record their measurements on the echo corelab e-CRF. For each subject, the mean LVOT VTI will be computed within each MARVEL 2 programmed mode. Since subject is the experimental unit, a paired t-test will be used to test the null hypothesis.

[Redacted]

[Redacted]

The following pre-specified subgroups will be evaluated using an analysis of variance (ANOVA) model: sex, geography (US versus outside of US), and participation in the original MARVEL study (yes versus no). For each ANOVA model the response will be the change in LVOT VTI between MARVEL 2 adaptive pacing and VVI pacing. The independent variable will be an identifier for subgroup.

If graphical assessments (e.g. Q-Q plots) of the distribution of change in LVOT VTI strongly suggest a deviation from normality, the Wilcoxon Signed-Rank test may be used as a sensitivity analysis.

[figure not shown]
7.5.5.5 Power Calculation

Background

The MARVEL study demonstrated a mean increase in LVOT VTI of 2.1 (cm) [95% CI: 0.7 – 3.5 cm] with associated standard deviation of 3.8 cm in MARVEL 2 adaptive pacing relative to VVI pacing in 31 subjects with high-grade AV block and with paired echocardiogram data. Specifically, as displayed in Figure 10, mean LVOT VTI increased from an average of 21.8 cm to 23.9 cm. The left panel of Figure 10 displays the LVOT VTI values for individual subjects (gray lines) and on average (dark blue lines) for the 31 subjects with high-grade AV block subjects in MARVEL with paired echo assessments in both pacing modes. The right-hand plot in Figure 10 displays the absolute change in LVOT VTI for MARVEL 2 adaptive pacing relative to the VVI pacing mode for individual subjects (red circles) and on average (blue circle). The right-hand plot also indicates that the lower 95% confidence interval for the mean change in LVOT VTI exceeded zero.

The increase of 2.1 cm in LVOT VTI observed in the MARVEL study with MARVEL adaptive mode relative to VVI pacing is consistent with historical studies during the 1980s evaluating cardiac output between DDD and VVI pacing modes. See for example, Labovitz, et al⁸, who observed a mean increase in LVOT VTI of approximately 2 cm with DDD pacing relative to VVI pacing in 26 patients with paired echocardiogram data in both DDD and VVI pacing modes.

[figure not shown]
Figure 10: LVOT VTI (cm) During VVI Mode and MARVEL Adaptive Mode (MARVEL Study)

Note: Error bars represent 95% confidence intervals for mean LVOT VTI by pacing mode (right panel) or in mean paired LVOT VTI value differences during MARVEL adaptive pacing relative to VVI pacing.

Power Calculation

As the sample size for the primary efficacy objective determines the number of subjects with normal sinus node function and persistent 3rd degree AV block with usable Holter data that are required for the study (at least 35 subjects), the power to reject the null hypothesis for the secondary objective was determined for a number of sample sizes as the protocol does not preclude study investigators from enrolling a higher number of subjects with normal sinus node function and persistent 3rd degree AV block nor account for the potential of missing echocardiogram data due to reasons such as improper

echocardiogram image acquisition, equipment malfunction, or subject refusal. The following assumptions were made for all power calculations:

1. Two-sided type I error rate = 0.05
2. Single analysis after all enrolled subjects have had an opportunity to complete the MARVEL 2 study procedures and have had their Holter data evaluated
3. Each subject will have paired echocardiogram available for analysis in both the MARVEL 2 adaptive mode and in VVI mode
4. The paired difference in LVOT VTI is normally distributed with a mean of 2.1 cm and a standard deviation of 3.8 cm in the population of potential patients with normal sinus node function and persistent 3rd degree AV block
5. A paired t-test will be the primary test statistic

Table 2 displays the study power for both the paired t-test and for the Wilcoxon Signed-Rank test when there are 30, 35, and 40 subjects with normal sinus node function and persistent 3rd degree AV block observed during Holter monitoring. Although the pre-specified analytical method to evaluate the null hypothesis will be the paired t-test, the Wilcoxon Signed-Rank test may be used as a sensitivity analysis if there is strong evidence the difference in LVOT VTI is not normally distributed.

Table 2: Power to Reject the Null Hypothesis for the Secondary Objective

Sample Size ¹	Statistical Method ²	Power (%)
30	Paired t-test	83.3
	Wilcoxon Signed-Rank	80.5
35	Paired t-test	88.8
	Wilcoxon Signed-Rank	86.8
40	Paired t-test	92.6
	Wilcoxon Signed-Rank	91.3

¹Number of subjects with paired LVOT VTI data available for analysis.

²Power for Wilcoxon Signed-Rank test based on the population LVOT VTI having an underlying normal distribution.

7.5.5.6 Determination of Subjects/Data for Analysis

All subjects with normal sinus node function and persistent 3rd degree AV block during Holter monitoring and with paired LVOT VTI measurements during MARVEL 2 adaptive pacing and VVI pacing will be included in the analysis. Note that as long as a subject’s predominant rhythm can be determined from the Holter recording, the subject may be included in this analysis as determination of predominant rhythm does not require device marker channel.

For *de novo* subjects, only echocardiogram data collected at the pre-hospital discharge visit will contribute to the analysis of the secondary objective. However, if a *de novo* subject is missing paired

echocardiogram on the day following their Micra procedure but have paired LVOT VTI data from their 1-month visit, the 1-month data will be used in the analysis if available.

7.5.5.7 Missing Data and Sensitivity Analyses

Missing Data

Given the relatively short duration of the study, missing data is not expected to be a serious issue. However, missing data may arise if a subject does not perform the echocardiogram or the echocardiogram is uninterpretable by the echo core lab. Note that both reasons for missing data may plausibly be considered independent to change in LVOT VTI.

If the level of missing data is an issue, tipping point methodology will be employed to evaluate the sensitivity of the statistical inference to the missing data. Specifically, all subjects with missing data will be imputed to have the mean change and standard deviation in LVOT VTI in the observed data then iteratively set to a smaller mean change value until the statistical inference changes (i.e. P-value exceeds 0.05). Additionally, stochastic methods may be employed to aid in interpreting the likelihood the tipping point would be met or exceeded by determining how likely the mean value for subjects with missing data would exceed the tipping point.

Additional Sensitivity Analysis

Since *de novo* subjects may have more than one visit in which echocardiograms are obtained, the secondary objective will also be evaluated utilizing all available echocardiogram data. Specifically, a mixed effects linear regression model will be used to account for correlation in outcomes within subject to determine the effect of MARVEL 2 pacing on change in LVOT VTI. For this model, change in LVOT VTI will be the response and the model will incorporate an intercept and a random effect for subject. The fixed effects for the intercept term will be used to quantify the effect of MARVEL 2 adaptive pacing on LVOT VTI.

[REDACTED]

[REDACTED]

[REDACTED]

[Redacted]

[Redacted]

[Redacted]

[Redacted]

[Redacted]

[Redacted]

[Redacted]

[Redacted]

[Redacted]

[Redacted]

[Redacted]

[Redacted]

[Redacted]

[Redacted]

[Redacted]

run;

[Redacted]

[Redacted]

[Redacted]

[Redacted]

[Redacted]

[Redacted]

[Redacted]

[Redacted]

[Redacted]

[Redacted]

[Redacted]

[Redacted text block]

[Redacted text block]

[Redacted text block]

[Redacted text block]

[Redacted text block]

[Redacted text block]

[Redacted text block]

[Redacted text block]

[Redacted text block]

[Redacted text block]

[Redacted text block]

[Redacted text block]

[Redacted text block]

[Redacted text block]

[Redacted text block]

[Redacted text block]

[Redacted text block]

[Redacted text block]

[Redacted text block]

[Redacted text block]

[Redacted text block]

[Redacted text block]

[Redacted text block]

[Redacted text block]

[Redacted text block]

[Redacted text block]

[Redacted]

[Redacted]

[Redacted]

[Redacted]

[Redacted]

[Redacted]

[Redacted]

[Redacted]

[Redacted]

[REDACTED]

[REDACTED]

[REDACTED]

[REDACTED]

[REDACTED]

[REDACTED]

[REDACTED]

[REDACTED]

[REDACTED]

[REDACTED]

[Redacted]

[Redacted]

[Redacted]

[Redacted]

[Redacted]

[Redacted]

[Redacted]

[Redacted]

[Redacted]

- [Redacted]

- [Redacted]

[Redacted]

[Redacted]

[Redacted]

[Redacted]

[Redacted]

[Redacted]

[Redacted]

[Redacted]

[figure not shown]
[Redacted]

[Redacted]

[Redacted]

[Redacted]

[Redacted]

